#### Descriptive analyses

Continuous variables will be summarised using descriptive statistics (i.e. numbers, means, standard deviations [SD], medians, first and third quartiles, minimum and maximum). The 95% 2-sided CIs of means will be calculated when appropriate using the standard method (standard normal distribution).

Categorical variables will be summarised by numbers and proportions. The 95% 2-sided CIs of proportions will be calculated when appropriate using the Clopper-Pearson exact method.

### **Within-group comparisons**

Within group differences will be evaluated by a paired t-test, a Wilcoxon signed-rank test or a linear mixed model with random intercepts (on the raw data or the rank data depending on the distribution of the variable of interest) for continuous variables. In case of categorical variables, McNemar's test or Cochran's Q test will be used according to the number of modalities of the variable.

Time-to-event endpoints will be expressed in weeks. For the description, Kaplan-Meier estimates (product-limit estimates) will be presented with a summary of associated statistics (number of events, number of censored data / median, Q1 and Q3 survival time / estimate rates of patients not presenting the event of interest at 6 weeks, 12 weeks, 6 months, 12 months and 24 months) including the corresponding two-sided 95% CIs. The Kaplan-Meier curve will also be presented.

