#### **4.4.2 Study setting**

The GP examines the patient and makes the diagnosis of CVD, based on clinical signs and symptoms. Patients who receive a diagnosis of CVD according to international guidelines who require conservative or invasive treatment can be included in the study. Duplex ultrasound or any other specific examination is not required to make the diagnosis, but could be done if needed according to routine clinical practice and recommendations. Each participating GP (120 GPs) will select approximately between 10 and 15 patients with CVD.

During the inclusion visit (V0), a treatment strategy will be proposed to the patient with confirmed CVD by the GP. The treatment can be conservative or invasive, depending on the severity of the disease. Patients awaiting invasive treatment may receive conservative treatment to alleviate symptoms. The choice of treatment modality is left to the discretion of the treating physician, in agreement with the patient and according to local policies. As this is an observational study, there will be no interference in the choice of treatment, and no restrictions will be imposed.

Commonly proposed conservative treatment options include compression therapy, and oral or topical venoactive drugs. If the GP decides that the patient needs an invasive treatment, then the patient will be referred to a venous centre. The specialist to whom the patient is referred, chooses the type of invasive treatment, as done in standard clinical care. The specialist may also prescribe conservative treatment to the patient, either while awaiting invasive treatment or in case invasive treatment is not deemed necessary.

[figure not shown]
Patients and their GP may decide to switch at any time between conservative treatments or to undergo an intervention as secondary/add-on treatment to conservative treatment.

Baseline data will be collected by the GP on the day of the V0. Follow-up visits, which are expected to take place within the scope of routine clinical practice, will be organized by the GP at defined timepoints after the V0: at 6 weeks, 12 weeks, 6 months, 12 months and 24 months of follow-up (V1-V5).

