### **9.2 Sample size**

Considering a Minimum Clinically Important Difference (MCID) of 5 points before/after treatment for the primary endpoint (CIVIQ-20 GIS), a default correlation of 0.5, and with an expected drop-out of 60% of patients in the conservative group and 25% in the invasive group, we propose the recruitment of 1650 patients (safe margin), to finally include minimally 1590 patients (power 90%).

Each investigator (120 GPs) will recruit approximately between 10 and 15 consecutive patients.

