### **Primary endpoint**

The analyses will be conducted in the AS.

To evaluate the change in the CIVIQ-20 GIS from V0 to a visit realized 12 weeks after the beginning of the treatment (or day of the intervention for patients in the invasive group) in each treatment group, we will compare the V0 value with the value at 12 weeks with a paired t-test or Wilcoxon signed-rank test depending on the distribution of GIS of CIVIQ-20 in each treatment group.

A mixed model could be conducted, with the GIS of CIVIQ-20 as the dependent variable, the visit as a fixed effect and time between V0 and the day of the intervention as covariate and paired on the patient in the invasive group.

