### **Secondary endpoints**

The analyses will be conducted in the AS, overall and by treatment group (conservative group, invasive group). Descriptive statistics and within-group comparative analyses could be done by subgroup of conservative treatment (venoactive drugs, compression, combination of both), or by subgroup of invasive treatment (sclerotherapy, foam sclerotherapy, surgery, thermal ablation (laser or radiofrequency), non-thermal ablation, and venous stenting), if relevant.

Descriptive statistics will be provided for patient characteristics at V0 (in terms of demographics, profession, clinical characteristics, personal and family history of CVD, treatment history, specific comorbidities), risk factors, concomitant treatment and description of treatment characteristics per visit in terms of type of treatment (initial referral from GP and whether they actually received the treatment), concomitant treatment, compliance (for conservative treatment group only).

The proportion of patients who received an intervention as secondary/add-on treatment to conservative treatment (in the conservative treatment group) and the proportion of patients who received a re-intervention (in the invasive treatment group) and number of re-interventions will be provided. If there is enough recurrence (minimum 20% of concerned patients), a Kaplan-Meier analysis could be considered. Time to event will be calculated from the start date of conservative treatment to the date of the secondary/add-on intervention in the conservative treatment group.

Time-to-re-intervention will be calculated from the date of the intervention to the date of the re-intervention in the invasive treatment group.

Patients who will reach the end of the study without receiving an intervention (in the conservative group) or a re-intervention (in the invasive treatment group) will have the time to event censored at the date of treatment discontinuation for any other cause (in the conservative group) or at the date of the end of the study if study ended (in conservative and invasive treatment group).

The change in the CIVIQ-20 GIS over time from V0 to each follow-up visit will be evaluated with the same methods as the primary endpoint.

The change in the clinical part of the CEAP classification over time from V0 to each follow-up visit will be described.

The change in the rVCSS over time from V0 to each follow-up visit will be evaluated with the same methods as the primary endpoint.

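### If the random-intercept mixed model is fitted jointly over V0 to V5, it imposes one correlation on visits 6 weeks to 24 months apart, and its standard errors for change from V0 can be wrong (minor)

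*Protocol*

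**What the plan says.** Under Within-group comparisons, Section 9.3.3 of the protocol lists the methods for continuous variables as "a paired t-test, a Wilcoxon signed-rank test or a linear mixed model with random intercepts", on raw or ranked data. The third option, "a linear mixed model with random intercepts", is the one at issue here.

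For the primary endpoint the same section commits to simple paired tests: "we will compare the V0 value with the value at 12 weeks with a paired t-test or Wilcoxon signed-rank test". The mixed model is optional there: "A mixed model could be conducted, with the GIS of CIVIQ-20 as the dependent variable, the visit as a fixed effect". Its covariate is the waiting time from V0 to intervention, it concerns the invasive group, and no covariance structure is given.

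Under Secondary endpoints, the change in CIVIQ-20 GIS "from V0 to each follow-up visit will be evaluated with the same methods as the primary endpoint". The rVCSS and symptom scores are handled likewise.

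Section 4.4.2 places the visits "at 6 weeks, 12 weeks, 6 months, 12 months and 24 months of follow-up (V1-V5"). Section 9.2 gives a single correlation for before against after treatment, "a default correlation of 0.5", and says nothing about other lags.

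**The concern.** A random intercept with independent, equal-variance residuals is a compound-symmetry model. It treats V0 and the 24-month visit as no less alike than V0 and the 6-week visit. The protocol itself gives reasons to doubt this:

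- The visits are very unequally spaced.
- Patients may change conservative treatment or add an intervention at any time (Section 4.4.2).
- A delay before intervention is expected in the invasive group (Section 4.4.2), so some early visits may precede the intervention and later ones follow it.

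If the model is fitted over all visits, one pooled error serves every change from V0. The standard errors, confidence intervals and p-values at individual visits can then be off. The long-term visits, which the rationale in Section 3 emphasises, are among those exposed.

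**Working it through.** **Inputs.** Visit times are weeks 0, 6, 12, 26, 52 and 104 (Section 4.4.2, months converted to weeks). The only correlation in the protocol is 0.5 (Section 9.2). Every other correlation below is an assumption. Data are taken as complete, with equal variances unless stated.

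**1. What the model implies.** Write y_ij = μ_j + b_i + e_ij with Var(b) = τ² and Var(e) = σ². Every visit has variance τ² + σ², every pair has covariance τ², and every change from V0 has variance 2σ². The fitted σ² is the mean visit variance minus the mean covariance over the 6 × 5 / 2 = 15 pairs of visits.

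**2. What is true.** Var(y_j − y_0) = Var_0 + Var_j − 2 Cov_0j. With equal variances,

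R_j = model SE / true SE = √[(1 − ρ̄) / (1 − ρ_0j)],

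where ρ̄ is the mean correlation over the 15 pairs. Coverage of a nominal 95% interval is 2Φ(1.96 R_j) − 1.

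**3. The protocol's own figure.** If 0.5 held at every lag, R_j = √(0.5/0.5) = 1.00 and coverage would be 95.0% at every visit. There would be no error.

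**4. Other patterns.**

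| Assumed correlation | ρ̄ | R at V1 (coverage) | R at V5 (coverage) |
|---|---|---|---|
| Mild decay, 0.6·(0.4/0.6)^(lag/104) | 0.508 | 1.09 (96.7%) | 0.91 (92.4%) |
| Decay, 0.75·(0.4/0.75)^(lag/104) | 0.583 | 1.23 (98.4%) | 0.83 (89.8%) |
| Exponential, 0.5^(lag/12) | 0.227 | 1.62 (99.9%) | 0.88 (91.5%) |
| V0 to post 0.5, post to post 0.7 | 0.633 | 0.86 (90.7%) | 0.86 (90.7%) |
| V0 to post 0.6 falling to 0.4, post to post 0.75 | 0.667 | 0.91 (92.6%) | 0.75 (85.6%) |

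Worked case, second row at V5: √[(1 − 0.583)/(1 − 0.40)] = √(0.417/0.60) = 0.83.

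Worked case, fourth row: ρ̄ = (5 × 0.5 + 10 × 0.7)/15 = 0.633, and √(0.367/0.5) = 0.86 at every visit.

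**5. Unequal variances.** Take mild decay with variances 1, 1, 0.9, 0.8, 0.7 and 0.6 from V0 to V5. V1 is then essentially right (R = 1.00, 94.9%), and V5 stays too narrow (R = 0.91, 92.7%).

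**6. Simulation cross-check.** A further decay pattern (correlation with V0 from 0.67 at 6 weeks to 0.36 at 24 months; 200 patients, 4,000 data sets) gave a V5 standard error 13% too small and a V1 standard error 22% too large. A nominal 5% test rejected in 8.6% at V5 and 1.6% at V1. The formula agrees: with ρ̄ about 0.51, √(0.49/0.64) = 0.875 at V5 and √(0.49/0.33) = 1.22 at V1.

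**7. Two visits only.** With V0 and one follow-up visit in 200 complete simulated pairs, the random-intercept model and the paired t-test gave the same standard error (1.0670 for both).

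**The case against.** The case against is strong, and most of it stands as a limit on the point.

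- **Committed tests.** The by-visit analyses of GIS, rVCSS and symptoms refer back to the primary method, a paired t-test or Wilcoxon test. The paired t-test estimates the variance of each change separately, and neither test pools error across visits.
- **Optional model.** The mixed model is optional and might be fitted to two visits at a time. With complete pairs it is then the paired t-test.
- **Wording.** The protocol does not say random intercepts only. A residual covariance structure could be added, and Section 9.3.3 leaves the description of methods to the SAP, which is not at hand.

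A reader might infer that the plan's late intervals are too narrow and its early ones too wide, with inflated false positives at 12 and 24 months. The documents do not support that as a general statement. It needs correlation that falls with time and roughly equal variances, and the protocol gives only the single value 0.5. Constant correlation gives no error, and the last two rows of the table make early intervals too narrow as well.

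What survives is that the protocol names a structure and does not leave it open, so a SAP that follows the text would inherit it. The model may also matter more than the word optional suggests. Section 9.1 states that the statistical model will adjust for the wait before intervention, and among the methods described only the mixed model carries that covariate.

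**Conclusion.** The point holds conditionally and is minor. It applies only if a mixed model is fitted jointly over more than two visits with a random intercept and independent, equal-variance residuals.

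In that case the 24-month standard error is about 9% to 17% too small under the three decay patterns in the table, and the 6-week one is 9% to 62% too large. Where post-treatment visits resemble each other more than V0, all visits can be too narrow, with 24-month coverage down to 85.6% in the worst pattern tried. In all six non-constant patterns calculated (five in the table and one with unequal variances), 24-month coverage fell below 95%, between 85.6% and 92.7%. A single visit can still come out right by coincidence.

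These sizes rest on assumed correlations and complete data. Section 9.2 expects drop-out of 60% and 25%. With incomplete data a wrong covariance can also affect the estimated visit means, which was not quantified here.

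**What to change.** In Section 9.3.3, Within-group comparisons, and correspondingly in the SAP before database lock: for any mixed model spanning more than two visits, replace the random-intercept specification by visit as a categorical fixed effect with an unstructured within-patient covariance, fitted by REML with Kenward-Roger degrees of freedom. Name in advance a fallback for non-convergence or small treatment subgroups: heterogeneous Toeplitz, or robust standard errors. The paired tests need no change.

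The cost is one line of text and 6 × 7 / 2 = 21 covariance parameters for six visits. Hundreds of patients per main treatment group support that easily, but small treatment subgroups may not, hence the fallback. Heterogeneous Toeplitz ties correlation to visit order and not to elapsed time. With visits this unevenly spaced it is a compromise, and robust standard errors would be a useful check on it. The text should also say how V-i enters such a model, because it has no fixed place in the visit sequence.

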### **Primary endpoint**

The analyses will be conducted in the AS.

To evaluate the change in the CIVIQ-20 GIS from V0 to a visit realized 12 weeks after the beginning of the treatment (or day of the intervention for patients in the invasive group) in each treatment group, we will compare the V0 value with the value at 12 weeks with a paired t-test or Wilcoxon signed-rank test depending on the distribution of GIS of CIVIQ-20 in each treatment group.

A mixed model could be conducted, with the GIS of CIVIQ-20 as the dependent variable, the visit as a fixed effect and time between V0 and the day of the intervention as covariate and paired on the patient in the invasive group.

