With progression to higher clinical stages of the disease, patients will seek appropriate treatment to alleviate symptoms. The treatment options nowadays are extended (Campbell 2020) and influenced by the disease severity, reimbursement policies, costs, geography and the preference of the surgeon (Guillaume 2020). Diminishing the signs and the symptoms of the disease, and preventing progression and recurrence are the main objectives for every treatment option. The treatment options range from conservative therapy, such as lifestyle changes, oral or topical venoactive drugs, or compression to more invasive treatments including sclerotherapy, surgery and endovenous techniques. Treatment guidelines have been prescribed according to the severity of the disease (Gloviczki 2011, Gloviczki 2012, Wittens 2015, Rabe 2013, Nicolaidis 2018, Nicolaidis 2020).

Several RCTs have provided evidence that venoactive drugs and compression therapy may reduce symptoms of CVD (Martinez-Zapata 2020, De Maeseneer 2022). The non-interventional, prospective

“VEIN Act Program” study has shown the effectiveness of conservative therapies to reduce CVD symptoms, but average follow-up was only 2.5 months (Bogachev 2019).

In order to evaluate the efficacy of the possible invasive treatments, a large number of Randomised Controlled Trials (RCTs) and meta-analyses have been conducted (Murad 2011, Siribumrunwong 2012, Hamann 2017). In many studies, anatomical success (occlusion rates) and postoperative side-effects such as pain, paraesthesia, and ecchymosis are the main outcomes. Surrogate outcomes, such as vein occlusion rates, stent patency, and changes in venous haemodynamics do not necessarily relate to a clinical change. In contrast, the number of publications including symptomatology and QoL as an outcome are limited. Only few studies have a long-term follow-up (Murad 2011, Eklöf 2014, Brittenden 2019, Kheirelseid 2018). Some studies with longer follow-up show controversial results: less favourable anatomical results (duplex ultrasound) did not result in any difference in clinical and QoL outcomes (Hamann 2017).

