#### 4.2 Primary endpoints

The primary endpoint is the change in the Global Index Score (GIS) of the Chronic Venous Insufficiency Quality of life questionnaire (CIVIQ-20) from V0 to a visit realized 12 weeks after the beginning of the treatment (or day of the intervention for patients in the invasive groups).

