### 5.2 Exclusion criteria

Patients meeting any of the following criteria will not be eligible for inclusion in the study:

- Patient with coagulation disorders such as thrombophilia and/or taking anticoagulation drugs,
- Pregnant or breastfeeding patient,
- Patient with severe Peripheral Arterial Occlusive Disease (POAD), with Ankle Brachial Index (ABI)  $< 0.8$ ,
- Patient with malignancy,
- Patient with neurological disorder or dementia,
- Patient taking regular treatment for CVD 3 months prior to inclusion (except painkillers or anti-inflammatory drugs if taken for reasons other than CVD),
- Patient in any other clinical study for any pharmaceutical product within 4 weeks preceding study inclusion,
- Patient with any comorbidity or situation preventing a follow-up of 2 years.

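### The invasive group's primary change from V0 can include pre-procedure change and ongoing conservative treatment, and the planned waiting-time adjustment does not separate them out

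*Protocol*

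**What the plan says.** **Baseline.** Protocol section 5.2 excludes a "Patient taking regular treatment for CVD 3 months prior to inclusion", apart from painkillers or anti-inflammatory drugs taken for other reasons. Section 5.1 requires a GP visit for CVD complaints. V0 is thus a symptomatic visit off regular CVD treatment.

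**The wait.** Section 4.4.2 expects a delay between referral and procedure, of unstated length. During it, "Patients awaiting invasive treatment may receive conservative treatment to alleviate symptoms". The venous centre may do the same: "The specialist may also prescribe conservative treatment to the patient, either while awaiting invasive treatment or in case invasive treatment is not deemed necessary". The usual options are compression and venoactive drugs, which are the conservative group's treatments. Section 3 says of them: "Several RCTs have provided evidence that venoactive drugs and compression therapy may reduce symptoms of CVD".

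**Endpoint and test.** Section 4.2 defines the change as running "from V0 to a visit realized 12 weeks after the beginning of the treatment (or day of the intervention for patients in the invasive groups". Section 7 places the invasive group's second value at V-i. Section 9.3.3 plans this for each group: "we will compare the V0 value with the value at 12 weeks", by a paired t-test or a signed-rank test according to the distribution.

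**The stated remedy.** Section 9.1 says without qualification that the statistical model adjusts for the time before the intervention. Section 9.3.3 offers a mixed model only as a possibility. Its terms are visit, and time from V0 to the intervention as a covariate, with pairing on the patient. No term covers conservative treatment.

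**Data planned.** Table 1 (section 4.6) schedules CIVIQ-20, treatment characteristics, conservative treatment compliance and concomitant treatment at V1 to V5 and V-i. Section 9.3.3 describes concomitant treatment, and limits the compliance summary to the conservative group.

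**The concern.** The study design (sections 1 and 4.4) sets out to assess the effectiveness of conservative and invasive treatments. For a patient who waits, the V0 to V-i change adds three parts: any change after a complaint-driven visit, any benefit of conservative treatment begun during the wait and still in use at V-i, and the effect of the procedure. The primary analysis reports only their sum.

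The first part is common to every uncontrolled before/after comparison, including the one in the conservative group. The second is specific to the invasive group, is expressly allowed, and can be described from data the study already plans to collect. If the sum is reported as the result of invasive treatment, improvement that preceded the procedure or came from the other group's treatment will be credited to it. Section 9.1 adds to the risk by telling the reader that the waiting period is adjusted for.

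**Working it through.** **1. Does the waiting-time covariate change the estimate?** Write the optional model for patient i at visit j (0 = V0, 1 = V-i) as

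Y_ij = α + β·visit_j + γ·w_i + u_i + e_ij,

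where w_i is the wait. The wait is the same at both visits, so within a complete pair

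D_i = Y_i1 − Y_i0 = β + (e_i1 − e_i0).

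The term γ·w_i cancels, and the estimate of β is the mean of D_i, the same quantity that the paired t-test uses.

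A numerical check used one simulated data set: 415 patients, waits spread from 2 to 26 weeks, half given conservative treatment worth 5 points, and a procedure effect of zero. The paired mean change was −1.107 (standard error 0.944), which is sampling variation around an expected −2.5. The visit estimate was −1.107 without waiting time, −1.107 with it, and −1.107 with a centred visit-by-wait interaction. All of this change arose without any procedure effect, and the model attributed it to visit.

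**2. How large could the contribution be?** The protocol does not say. Let b be the share of invasive patients on conservative treatment begun during the wait and still in use at V-i, and c its mean effect on GIS. The contribution is b × c. The only GIS figure in the protocol is the MCID of 5 points (section 9.2). It is used here as c for illustration; it is not an estimate of the conservative effect.

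- b = 25%: 0.25 × 5 = 1.25 points
- b = 50%: 0.50 × 5 = 2.5 points
- b = 100%: 1.00 × 5 = 5 points

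**3. Would the paired test detect such a change?** This needs a number of completers and an SD of differences, and section 9.2 gives neither. The planned minimum of 1590 cannot be reproduced from the stated inputs, but it can be solved backwards if completers are assumed equal in the two groups:

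n/0.40 + n/0.75 = 3.833n = 1590, so n ≈ 415 per group.

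For a paired test with 90% power, SD = 5 × √414.8 / (1.960 + 1.282) ≈ 31.4. With the stated correlation of 0.5, the SD of differences equals the SD of a single score. A smaller SD of 20 and a smaller group of 200 are shown as a range. The probability of a two-sided 5% result when the procedure adds nothing is Φ(m√n/SD − 1.96) + Φ(−m√n/SD − 1.96), with m = 5b:

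| b | m | n = 415, SD 20 | n = 415, SD 31.4 | n = 200, SD 20 | n = 200, SD 31.4 |
|---|---|---|---|---|---|
| 25% | 1.25 | 0.247 | 0.128 | 0.143 | 0.087 |
| 50% | 2.5 | 0.721 | 0.368 | 0.424 | 0.203 |
| 100% | 5 | 0.999 | 0.900 | 0.942 | 0.615 |

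These figures show only that the test cannot tell the sources apart. They do not forecast b, c or the procedure's effect, and they contest no sample size.

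**The case against.** Change from diagnosis to 12 weeks after the procedure is a legitimate care-pathway measure in a study that does not interfere with treatment. The primary objective concerns the evolution of QoL, section 3 speaks of description and association, section 9.3.3 calls the analyses mainly descriptive, and no between-group test is planned. Section 9.3.3 also plans GIS change from V0 to every follow-up visit by group, so early change in the invasive group will be partly visible, though not aligned to the procedure date. Group rules and further subgroups are left to the SAP. All of this stands. It is why the endpoint should be kept, and why the absence of a particular table from the protocol is not itself an error.

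It does not answer two things: the effectiveness wording of the design sections, and the claim of adjustment in section 9.1, which section 9.3.3 makes optional and which the named covariate cannot deliver.

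Three stronger readings are tempting and not supported:

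- **The invasive result contains a full conservative-treatment effect.** At group level that needs every patient to be treated while waiting and still treated at V-i. The protocol says only that such treatment is allowed.
- **The invasive versus conservative comparison is biased.** No such test is planned; the risk lies in informal side-by-side reading.
- **The change from the last pre-procedure value to V-i is the intervention effect.** That value exists only for patients who waited long enough and attended a visit. If conservative treatment stops after the procedure, the segment is the procedure's gain less the benefit lost.

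**Conclusion.** The point holds as a matter of interpretation and of an adjustment that is claimed but not delivered. The invasive group's primary change can include change before the procedure and benefit from conservative treatment still in use at V-i. Its size is unknown. The 1.25 to 5 points above rest on an assumed share and on the MCID standing in for the conservative effect, and the contribution is smaller if that treatment stops before V-i. Section 3 supports an effect on symptoms and gives no GIS figure.

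The algebra on waiting time rests on no such assumption: for complete pairs, a patient-constant main effect leaves the V0 to V-i contrast unchanged. The conflict between sections 9.1 and 9.3.3 is in the text. The conclusion does assume that the SAP keeps patients who were treated while waiting in the invasive group, as section 4.4.2 suggests. V0 is untreated only as to regular CVD treatment. The change is worth making before the SAP is final, but it does not invalidate the endpoint.

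**What to change.** 1. **Keep V0 to V-i as the primary endpoint.** State in sections 4.2 and 9.3.3 that for the invasive group it describes the whole care pathway from inclusion, not the effect of the intervention alone.

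2. **Reconcile section 9.1 with section 9.3.3.** Either remove the claim of adjustment or specify a model that can deliver it, for example with a visit-by-waiting-time interaction and a term for conservative treatment. That term must vary by visit or interact with visit, since a patient-constant one cancels as well. With a centred interaction the visit estimate is still the mean change, so report the change at stated waits and by conservative treatment use.

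3. **Add one supportive table for the invasive group.** Show the V0 to V-i change by conservative treatment during the wait (yes/no) and at V-i (yes/no). Where a CIVIQ-20 value after V0 and before the procedure exists, split the change at that value. Report the number and characteristics of patients with and without it.

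**Cost.** Two text edits and one table, from assessments already in Table 1. Visits and care are unchanged. The downside is that the split covers a subset selected by longer waits and attendance, and its second segment is not a pure intervention effect. It should support, and not be the sole basis for, statements about the intervention.

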## **9. Statistics**

### **9.1 Risk of bias**

The results obtained during this study may be biased through selection of the treating physicians and the willingness of patients to participate. To minimize the bias related to GP representativity, GPs will be selected throughout Belgium. The GPs will be asked to offer the study to all patients who meet the eligibility criteria, and to select consecutive patients whenever possible. GPs will receive a training before the start of the study.

The statistical model will adjust for the period during which the patients in the invasive treatment group had not yet received the intervention (i.e., the time between inclusion at V0 and the day of the intervention) (See [Section 9.3 Analysis](#)).

Patients lost to follow-up may cause attrition bias. To minimize this bias, efforts will be made to contact the patients if they are lost to follow-up.

To minimize the risk of measurement bias, each GP will receive a training on the use of the assessment instruments (CEAP, rVCSS, CIVIQ-20, VAS) before the site activation.

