### 9.3.2 Population for analyses

The following analysis population will be considered:

- Included Set (IS): This set corresponds to all patients included for the study and with an Informed Consent Form (ICF) signed.
- Analysis Set (AS): This set corresponds to all patients from the IS with at least one follow-up visit (i.e. with at least a date of visit completed for visits V1, V2, V3).

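### Section 9.1 promises adjustment for the wait before the intervention, but the optional model in Section 9.3.3 does not deliver it: waiting time as a main effect leaves the complete-pair change unadjusted

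*Protocol*

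**What the plan says.** Section 9.1 (Risk of bias) lists a firm control: "The statistical model will adjust for the period during which the patients in the invasive treatment group had not yet received the intervention". It refers the reader to Section 9.3 for the method.

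Section 9.3.3 (Primary endpoint) gives the method for each treatment group: "we will compare the V0 value with the value at 12 weeks with a paired t-test or Wilcoxon signed-rank test". Neither test takes a covariate. For the invasive group it then adds an option: "A mixed model could be conducted, with the GIS of CIVIQ-20 as the dependent variable", with "the visit as a fixed effect and time between V0 and the day of the intervention as covariate and paired on the patient". No visit-by-waiting-time term is named, and no score taken shortly before the intervention is used.

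Section 4.4.2 expects a delay between referral and intervention and says of that period: "Patients awaiting invasive treatment may receive conservative treatment to alleviate symptoms".

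**The concern.** There are two problems. First, Section 9.1 says the model *will* adjust, while Section 9.3.3 says a model *could* be fitted beside tests that cannot adjust. Second, the optional model, as written, does not adjust the quantity of interest. The primary quantity is a change within patients, whereas waiting time differs only between patients.

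At stake is how the invasive-group result is read. The change from V0 to V-i is the sum of what happens during the wait (drift, regression to the mean, any bridging conservative treatment) and what happens after the intervention. Section 9.1 identifies the first part as a risk of bias and says it is handled. If the optional model is run and its visit estimate is called adjusted, the label would be wrong. Section 9.3.3 also applies the primary-endpoint methods to the GIS over time, the rVCSS and symptoms, so the same model carries over to those endpoints.

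**Working it through.** The protocol gives no figure for this adjustment, so there is none to reproduce. The sample size in Section 9.2 does not bear on it.

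**Inputs from the protocol**
- Outcome: GIS. Fixed effect: visit (Section 9.3.3, Primary endpoint).
- Covariate: "the time between inclusion at V0 and the day of the intervention" (Section 9.1), which is one value per patient.
- Pairing on the patient; Section 9.3.3 (Within-group comparisons) gives "a linear mixed model with random intercepts".
- Analysis Set: "all patients from the IS with at least one follow-up visit" among V1 to V3 (Section 9.3.2). V-i is not required, so incomplete pairs can occur.

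**Algebra.** For patient i with wait w(i), patient effect u(i) and errors e:
- V0: Y0(i) = a + g·w(i) + u(i) + e0(i)
- V-i: Y1(i) = a + b + g·w(i) + u(i) + e1(i)
- Difference: D(i) = b + e1(i) − e0(i)

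The term g·w(i) cancels whatever the value of g. With complete pairs the estimate of b is the mean of D and its SE is SD(D)/√n, exactly as in the paired t-test.

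If d·w(i) is added at V-i only (the interaction), then D(i) = b + d·w(i) + e1(i) − e0(i). Now b is the change at zero wait. At the mean wait the model returns the mean of D, which is the unadjusted change.

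**Numerical check, complete pairs.** The inputs are assumptions, not protocol figures: 600 pairs; mean wait 10 weeks; change of -10 points minus 0.4 per week waited; baseline rising by 0.5 points per week of wait; patient and error SDs of 14 each, so the correlation given wait is 14²/(14² + 14²) = 0.5. Random-intercept REML fits:

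| Model | Estimated change | SE |
|---|---|---|
| Paired mean difference | -13.490193 | |
| Visit only | -13.490193 | 0.8093 |
| Visit + wait (as written) | -13.490193 | 0.8093 |
| Visit × wait, at zero wait (true value -10) | -10.12 | 1.44 |
| Visit × wait, at mean wait | -13.49 | 0.80 |

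**Numerical check, incomplete pairs.** Same assumptions, 300 patients, 25 replicates. The 25% is the invasive-group drop-out in Section 9.2; the 60% is the conservative-group figure, used here only as an extreme.

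| V-i missing | Mean absolute shift from adding wait | Mean estimate with wait as main effect |
|---|---|---|
| 25%, at random | 0.03 | -13.60 |
| 25%, dependent on wait | 0.39 | -13.12 |
| 60%, dependent on wait | 0.66 (maximum 1.17) | -13.23 |

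The estimates stay near -13 although the change at zero wait was set to -10. The shift arises because patients without V-i contribute only a V0 value, and the covariate changes how their level is compared with the rest. It does not remove change that accrues during the wait.

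**How large the waiting part could be.** The protocol gives neither the length of the wait nor the change during it. If change accrues at 0 to 0.4 points per week, the waiting part is 0 to 0.4 × 10 = 4 points at a mean wait of 10 weeks, and 0 to 0.4 × 15.5 = 6.2 points at 15.5 weeks. The minimum clinically important difference in Section 9.2 is 5 points. These are illustrations only.

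**The case against.** The strongest case on the other side has four parts.

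- **The endpoint includes the wait by definition.** It runs from V0 to 12 weeks after the intervention, the named primary test is unadjusted, the analyses are mainly descriptive, and the mixed model is optional. This stands, and it limits the severity. A reader might infer that the primary invasive result will be reported as adjusted when it is not. The protocol does not say so; mislabelling arises only if the optional model is run and its visit estimate is called adjusted.
- **The cancellation is not absolute.** A reader might infer that the covariate can never move the estimate. That holds for complete pairs only. The Analysis Set admits patients without V-i, and small shifts then occur. This stands as a limit on the claim, but those shifts are not the promised adjustment.
- **An interaction is not a full remedy.** A reader might infer that adding it isolates the effect of the intervention. It does not: it shows how the change varies with wait. Patients who wait longer may differ in other respects, zero wait may be an extrapolation, and at the mean wait the interaction model gives back the unadjusted change. This stands and shapes the fix.
- **The SAP may settle the details.** Calling waiting time a covariate does not strictly exclude an interaction, and an SAP that is not shown could add one. But the protocol itself lists the model terms, and a main effect is their plain reading. The clash between *will* and *could* would remain in the protocol in any case.

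**Conclusion.** Wrong as written; should be fixed. Sections 9.1 and 9.3.3 disagree on whether an adjusting model will be fitted, and the model described does not adjust the change from V0 to V-i.

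For complete pairs the adjustment is nil by algebra, given one waiting time per patient, a main effect and random intercepts. For incomplete pairs, average shifts of 0.03 to 0.66 points were seen under the assumed scenarios, caused by missing V-i values and not by removal of waiting-period change. The size of the waiting part in this study is unknown.

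The documents do not show that the primary paired result is invalid for its own definition. It is a valid total change from V0. What fails is the statement in Section 9.1 that the period before the intervention is adjusted for.

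**What to change.** Reconcile Sections 9.1 and 9.3.3 in one of two ways.

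**(a) Keep the adjustment, as a supporting analysis.** In Section 9.3.3, commit to the mixed model and add a visit-by-waiting-time interaction. Report the change at a stated short wait and at the mean wait, and describe the result as how the change varies with wait. Add a supporting analysis that splits the change at the last available GIS before the intervention (V0, V1 or V2), and state how many patients contribute. Reword Section 9.1 to match.

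**(b) Withdraw the claim.** Delete the adjustment sentence from Section 9.1 and label the invasive-group result as total change from V0, including the waiting period and any conservative treatment given in it.

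Option (a) costs one model term and one table. Precision at short waits is lower: in the check the SE at zero wait was 1.44 against 0.81, about 1.8 times as large. The assessments and dates are already scheduled, but V1 and V2 may not take place, V-i replaces any visit it overlaps, and patients treated before V1 have only V0 beforehand. The split therefore rests on those with a follow-up visit before the intervention. Option (b) costs two sentences.
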